10.3.1.2. Rate of CR/CR_h

CR/CR_h is defined as the rate of subjects with the best response of CR or CR_h. Since CR_h is not initially defined in the modified IWG criteria and therefore is not available from the investigator assessment. The analyses of CR/CR_h will be based on the IRAC assessment.

Number and percentage of subjects with CR/CR_h and the 2-sided exact binomial 95% CI will be summarized for Phase 1, Phase 2, and the combined Phase 1/2 in the FAS.

10.3.1.3. Rate of CR/CR_i/CR_p

This key secondary efficacy endpoint of CR/CR_i/CR_p is defined as the rate of subjects with the best response of CR, CR_i, or CR_p. The CR/CR_i/CR_p rate will be summarized by the percentage of responses primarily in the FAS with 2-sided exact binomial 95% CI for Phase 1 dose escalation, Part 1 Expansion, the combined Phase 1, Phase 2, and the combined Phase 1/2 for the FAS as described in items 1 to 5 of [Section 5.1](#).

The following sensitivity analyses will be performed:

- (1) CR/CR_i/CR_p rate in EAS;
- (2) CR/CR_i/CR_p rate assessed by IRAC in the FAS.

10.3.1.4. Duration of Response

Among subjects who have a response of CR, CRi, CRp, PR, or mCR/MLFS by investigator assessment, DOR will be calculated as the date of the first documented response to the date of the first documented disease relapse, progression or death due to any cause, whichever occurs first. Subjects without relapse, progressive disease, or death due to any cause will be censored at the date of the last adequate response assessment.

Table 3: Censoring Rules for Duration of Response

End Date for Duration of Response	Censored (Y,N)	Scenarios
The earliest of death date, relapse date, and progression date	N	A subject has less than 2 consecutive missing response assessments prior to a documented death, relapse, or progression which is before any subsequent anti-cancer therapy.
The last adequate response assessment date before missing assessments	Y	A subject has 2 or more consecutive missing response assessments prior to a documented death, relapse, or progression.
The last adequate assessment date	Y	If a subject did not die, did not relapse or progression, and did not receive any subsequent anti-cancer therapy.
The last adequate assessment date on or prior to the start of subsequent anti-cancer therapy	Y	If a subject did not die, did not relapse or progression on or prior to subsequent anti-cancer therapy.
The last adequate assessment date on or prior to the start of subsequent AML therapy	Y	If a subject died, relapsed, or had disease progression after receiving subsequent anti-cancer therapy.
1) If response assessment after a single documented progressive disease /relapse shows response including CR, CRi, CRp, PR, mCR/MLFS, the relapse/progression before documented response is considered as NE. 2) Subsequent anti-cancer therapy in this table excludes HSCT.		

DOR will be summarized primarily based on investigator assessment. The DOR will be analyzed using KM methods and KM curves. The 25th percentile, median and 75th percentile of the response duration with 2-sided 95% CI will be provided for overall responders in the FAS for Part 1 Expansion, the combined Phase 1, Phase 2, and the combined Phase 1/2 as described in items 2 to 5 of [Section 5.1](#). KM estimates at 3, 6, 9 and 12 months will be provided at individual time points. Due to the limited sample size of each total daily dose group, DOR will not be analyzed for Phase 1 dose escalation.

The sensitivity analyses for DOR in overall responders regarding censoring rules will be conducted for the combined Phase 1, Phase 2, and the combined Phase 1/2:

- Subjects who undergo HSCT will be censored at the last adequate assessment prior to HSCT;
- Subjects with 2 or more consecutive missing response assessments prior to an event (death, relapse or disease progression) and/or subjects with subsequent anti-cancer therapies prior to an event will be considered as events at the event date by ignoring the missing assessments and subsequent anti-cancer therapies

In addition, a sensitivity analysis for the confirmed progression will be performed to examine the impact of unreliable progressive disease assessment where a single documented relapse or progression immediately followed by a response will be considered as the first relapse/progression.

The DOR will be analyzed based on the IRAC adjudicated response to support the primary results by investigator assessment. Sensitivity analyses regarding censoring rules will be performed for IRAC DOR.

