### **Endpoints**

**Overall response rate (ORR):** ORR is defined as the rate of CR, CRp, mCR [MLFS], CRi, and PR.

**Complete remission rate (CRR):** CRR is defined as the rate of CR.

**Duration of response (DOR):** Among subjects who have a response of CR, CRp, mCR, CRi, or PR, DOR will be calculated as the date of the first occurrence of response to the date of documented disease relapse, progression or death, including subjects that discontinue AG-221 treatment to receive bone marrow transplantation. Kaplan-Meier methods will be used to estimate DOR, and subjects without relapse, progression or death will be censored at the last response assessment date.

**Duration of complete remission (DOCR):** Among subjects who have a response of CR, DOCR will be calculated as the date of the first remission to the date of documented disease relapse or death, including subjects that discontinue AG-221 treatment to receive bone marrow transplantation. Kaplan-Meier methods will be used to estimate DOCR, and subjects without relapse or death will be censored at the last response assessment date.

**Time to response (TTR):** Time to response will be assessed from the date of first dose to the date of first occurrence of response, which includes CR, CRp, mCR/MLFS, CRi, and PR. Subjects without a response will be censored at the date of last response assessment.

**Time to Best Response (TTBR):** Time to best response will be assessed from the date of first dose to the date of first occurrence of best response. Subjects without a response will be censored at the date of last response assessment.

**Time to complete remission (TTCR):** Time to complete remission will be assessed from the date of first dose to the date of first remission (CR). Subjects without a remission will be censored at the date of last response assessment.

**Event-free survival (EFS):** Event-free survival will be calculated from the date of first dose to the date of relapse, progression or death, whichever occurs first. Subjects without an EFS event will be censored at the last response assessment date. Kaplan-Meier methods will be used to estimate EFS, including subjects that discontinue AG-221 treatment to receive bone marrow transplantation.

**Overall survival (OS):** Overall survival is defined as the time from first dose to the date of death. Subjects who are alive at the analysis cutoff date will be censored at the last contact date.

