10.3.2.1. Event-Free Survival

Event-free survival is defined as the interval from the date of the first dose to the date of documented relapse, progression, or death due to any cause, whichever occurs first. Subjects without an EFS event will be censored according to the rules in [Table 3](#). Subjects who only have a baseline record will be censored at date of the first dose.

The analysis methods for EFS are similar to those for DOR. The KM method will be used to estimate the EFS probabilities at 3, 6, 9 and 12 months. The EFS based on IRAC assessment will also be analyzed for Phase 2 R/R AML subjects.

EFS will be analyzed in the FAS for Part 1 Expansion, the combined Phase 1, Phase 2, and the combined Phase 1/2. Due to the limited sample size of each total daily dose group, EFS will not be analyzed for Phase 1 dose escalation.

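### SAP Table 3, applied to EFS, censors events after new anti-cancer therapy that the protocol counts; the change is undeclared, and no EFS analysis that counts them is explicitly planned

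*SAP*

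**What the plan says.** Protocol 12.5.7 (Endpoints) defines the endpoint: "Event-free survival will be calculated from the date of first dose to the date of relapse, progression or death, whichever occurs first". It censors only subjects who have no such event, at their last response assessment, and makes no exception for new therapy.

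SAP 10.3.2.1 keeps the same events, with death from any cause, and then says: "Subjects without an EFS event will be censored according to the rules in" Table 3. That table sits in SAP 10.3.1.4 and is titled for DOR. Its only uncensored row requires fewer than two consecutive missing assessments "prior to a documented death, relapse, or progression which is before any subsequent anti-cancer therapy". A later row covers the opposite case, "If a subject died, relapsed, or had disease progression after receiving subsequent anti-cancer therapy", and sets the end date at "The last adequate assessment date on or prior to the start of subsequent AML therapy". A table note adds: "Subsequent anti-cancer therapy in this table excludes HSCT".

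SAP 10.3.1.4 also plans a DOR sensitivity analysis in overall responders in which "subjects with subsequent anti-cancer therapies prior to an event will be considered as events at the event date". For EFS, SAP 10.3.2.1 says only: "The analysis methods for EFS are similar to those for DOR". SAP 13 lists three changes from the protocol's statistical section, and this is not one of them.

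**The concern.** Table 3 was built for DOR, where everyone at risk has responded. EFS puts every treated subject at risk, including those who never respond. Protocol Table 7 classes resistant disease as treatment failure, but it is not an EFS event. Relapse requires an earlier remission or leukemia-free marrow, and progression should be confirmed at least a month apart. A subject with persistent leukemia can therefore move to another drug with no EFS event on record and then die. The protocol counts that death; Table 3 censors the subject before the switch.

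At stake are the EFS curve, its median and the 3-, 6-, 9- and 12-month rates. If subjects who switch fare worse than those who stay, the censoring is informative and the curve sits too high. Whatever the direction, it is not an estimate of the endpoint the protocol defines.

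**Working it through.** **Text comparison, by type of subject**

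1. Relapse or progression documented before new therapy, with fewer than two consecutive missed assessments: an event under the protocol and under the first row of Table 3. No conflict.
2. HSCT, then an event, with no other therapy: HSCT does not trigger the rule, so there is no conflict from it. Protocol 12.5.7 likewise keeps transplanted subjects in the main EFS analysis and makes censoring at transplant the sensitivity analysis.
3. New non-HSCT therapy without a documented relapse or progression, then relapse, progression or death: an event under the protocol, censored under Table 3. This is the conflict.

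SAP 10.3.2.1 does not settle group 3. It sends only subjects without an EFS event to Table 3. Read literally, a subject who dies after a switch has an event and never reaches the table. Table 3 read on its own reclassifies that death as censored. Two programmers could produce different curves.

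**Illustration of direction and size**

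The plan states no EFS figure, so there is none to reproduce. Inputs:
- Assessment interval 28 days (Protocol 10.8.2), or 28/30.4 = 0.92 months (SAP 15.1.1 conversion).
- Assumed, not in the documents: on-drug median m of 4 or 6 months; share p switching before a documented event, 10% to 40%; post-switch hazard r times the on-drug hazard, 0.5 to 5.

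On-drug hazard λ = ln 2/m. Switch hazard σ = λp/(1−p), which makes a proportion p switch first. Post-switch hazard h = rλ. With all events counted and a = λ + σ,

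S(t) = e^(−at) + [σ/(a−h)]·(e^(−ht) − e^(−at)).

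For m = 4, p = 0.3, t = 6: λ = 0.1733, σ = 0.0743, a = 0.2476, e^(−at) = 0.2264.
- r = 3: h = 0.5199; S = 0.2264 + (0.0743/−0.2723)(0.0442 − 0.2264) = 0.276.
- r = 0.5: h = 0.0866; S = 0.2264 + (0.0743/0.1609)(0.5946 − 0.2264) = 0.396.
- r = 1: S = e^(−6λ) = 0.354.

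A simulation of 200,000 subjects per scenario, censoring switchers at the last 28-day assessment before the switch for the Table 3 version, agrees with these values within simulation error:

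| m (months) | p | r | Median, all events / Table 3 | 6-month EFS, all events / Table 3 |
|---|---|---|---|---|
| 4 | 10% | 3 | 3.81 / 3.96 | 33.1% / 35.0% |
| 4 | 30% | 3 | 3.42 / 3.88 | 27.7% / 34.3% |
| 4 | 30% | 1 | 3.99 / 3.86 | 35.2% / 34.0% |
| 4 | 30% | 0.5 | 4.34 / 3.88 | 39.6% / 34.2% |
| 6 | 30% | 3 | 5.12 / 5.85 | 43.8% / 49.1% |
| 6 | 30% | 0.5 | 6.45 / 5.81 | 52.3% / 48.9% |

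Across all scenarios with r from 2 to 5, Table 3 reads higher by about 0.1 to 1.4 months in the median and 1 to 12 points at 6 months. With r = 1 it reads 0 to 2 points lower at 6 months, because censoring is back-dated to the last assessment. With r = 0.5 it reads about 1 to 8 points lower.

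**The case against.** Protocol 12.3 and 12.5.7 both leave censoring detail to the SAP, and censoring at new therapy is a common convention. This carries some weight, but a rule that turns a protocol-defined death into a censored observation goes beyond detail. The protocol's own handling of transplant runs the other way.

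The statement that EFS methods resemble those for DOR may be meant to bring the DOR sensitivity analysis with it. It may, but SAP 10.3.2.1 does not say so, and that analysis is scoped to responders.

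A reader might infer that subjects who leave AG-221 because it failed are removed just before their event. The documents do not support that. Protocol 10.8.3 makes confirmed progression the usual route off drug for failure, and it is dated to its first appearance, so it normally precedes the new therapy and stays an event. The others are censored at the last assessment before the switch, which need not be close to the event.

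A reader might also infer that EFS is shown to be overstated. A model that places each switch in the second half of the subject's own event-free time gives medians of 4.35, 4.75 and 5.35 months against a true 4 for 10%, 20% and 30% switching. It ties the switch to the coming event, so the upward sign is assumed, not found.

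Removing this row alone would also not restore every event. A subject who switches and dies later may have two or more missed assessments and be censored under that row instead.

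**Conclusion.** The conflict between the protocol's EFS definition and Table 3 is in the text and does not depend on any simulation. It concerns subjects who start non-HSCT therapy without a documented relapse or progression and later have an event. The documents do not say how many there are. The change is undeclared in SAP 13, the cross-reference in SAP 10.3.2.1 is unclear, and no EFS analysis that counts these events is explicitly planned.

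Overstatement is the expected direction if these subjects do worse after switching. Neither direction nor size can be fixed from the documents, and the sign reverses if the next therapy works. The figures above rest on assumed exponential times, switching shares and hazard ratios.

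The consequence is bounded. EFS is among the other secondary endpoints of a single-arm estimation study and has no decision rule. ORR does not use Table 3, and OS (SAP 10.3.1.5) has its own censoring rule and counts deaths after a switch. The point deserves correction but does not threaten the primary result.

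**What to change.** In SAP 10.3.2.1, specify an EFS analysis that follows Protocol 12.5.7: count the first relapse, progression or death on its date, ignoring both subsequent anti-cancer therapy and missed assessments. This is the second DOR sensitivity bullet of SAP 10.3.1.4 extended to EFS, for investigator assessment and for the IRAC EFS analysis already planned in Phase 2 R/R AML. Preferably make it the main EFS analysis and keep the Table 3 version as sensitivity; at minimum name it as an EFS sensitivity analysis. State whether Table 3 overrides an EFS event or applies only to subjects who have none. List the Table 3 censoring of EFS in SAP 13.

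The cost is SAP wording and one extra run, with a possibly less favourable EFS. Protocol 7.1.4 provides for follow-up of disease status, survival and new therapy after discontinuation. The Phase 2 schedule, however, marks post-treatment response evaluation only at end of treatment and in HSCT follow-up. Relapse or progression after a switch may therefore be less completely recorded than death, and the report should say so.

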### **10.8.3. Assessment of Response Criteria**

Evidence supports that cancer-associated IDH mutations block normal cellular differentiation and promote tumorigenesis via the abnormal production of 2-HG, a potential oncometabolite (Figure 3). AG-221 may produce antitumor effects by reversing the differentiation block induced by the IDH2 mutations and promoting appropriate cellular differentiation.

The response pattern seen with such mechanism of action may extend beyond the typical time course of responses seen with cytotoxic agents, and can generate a clinical response after an initial increase in the number of immature monocytes or blast cells, and increase in cellularity in the bone marrow, onset of cytopenia after initial rise in platelets, or appearance of differentiation-like syndrome.

Standard assessment criteria developed based on the experience from the cytotoxic chemotherapeutic agents may not provide a complete and accurate response assessment for this novel class of IDH2 inhibitors. Therefore, in the setting where a subject's assessment shows signs similar to progression within the first 2 cycles, caution should be exercised in discontinuing study drug, and a discussion with the Medical Monitor is required, especially in situations where the subject's clinical condition is stable as supported by, but limited to, absence of signs and symptoms of rapid deterioration indicating disease progression and/or general condition is stable or improving.

**Note** that for subjects enrolled in the Phase 1 portion of the trial, the C1D15 bone marrow evaluation should not be used to determine study treatment continuation status in any subject.

Subjects who experience progression of disease (PD) per the applicable response criteria should have assessment of the disease repeated 28 days later in order to confirm PD with option of continuing treatment as described above while awaiting for confirmation. If repeat evaluation confirms PD, subjects will discontinue study treatment and proceed to the survival follow-up phase (see Table 6 for general guidance).

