**Table 6: Disease Assessment and Treatment after 1st Evidence of Disease Progression**

	Clinically Stable		Clinically Unstable	
	Disease Assessment 	Treatment	Disease Assessment 	Treatment
1st evidence of PD or signs of differentiation like syndrome	Repeat assessment 28 days after first sign of progression for confirmation	Continue study treatment at the Investigator's discretion while awaiting for confirmatory assessment	Repeat assessment 28 days after first sign of progression for confirmation if possible	May discontinue study treatment at Investigator's discretion while awaiting for confirmatory assessment
If repeat evaluation shows SD, PR, or CR	Continue regularly scheduled assessment as per schedule of event	Continue study treatment	Continue regularly scheduled assessment as per schedule of event	Continue study treatment
If repeat evaluation confirms PD	No additional assessment required	Discontinue study treatment	No additional assessment required	Discontinue study treatment

Subjects in the dose escalation phase and Part 1 Expansion will have the extent of their disease assessed and recorded at screening, on Days C1D15, C2D1, and C3D1, every 56 days thereafter while on study drug treatment, independent of dose-delays and/or dose interruptions, and/or at any time when progression of disease is suspected.
 
Subjects in the Phase 2 portion of the trial will have the extent of their disease assessed and recorded at screening, on C2D1, every 28 days thereafter through 12 months and then every 56 days while on study drug treatment, independent of dose-delays and/or dose interruptions, and/or at any time when progression of disease is suspected.
				

**Note** that subjects with stable or progressive disease may continue to receive study treatment with AG-221 at the discretion of the Investigator and with Medical Monitor approval.

The following criteria outlined in [Table 7](#), [Table 8](#), [Table 9](#) and [Table 10](#) will be used to assess response to treatment for subjects with AML ([Table 7](#) and/or [Table 8](#)) and MDS ([Table 9](#) and [Table 10](#)). For subjects with other IDH2-positive hematologic malignancies other appropriate response criteria for the malignancy should be used.

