**Table 8: Criteria for Stable Disease and Progressive Disease for Acute Myelogenous Leukemia**

Category	Response criteria
Stable disease	Failure to achieve a response and not meeting the criteria for disease progression
Disease progression (defined only for subjects who have previously attained PR or SD)	
Progression should be confirmed by 2 consecutive assessments separated by at least 1 month.
 
Development of new biopsy-confirmed extramedullary disease since last disease evaluation
 
The date of progressive disease is defined as the first date of progression.
 
Progression is defined as the following:
 
For patients with 5 to 67% bone marrow blasts at nadir:
 
 
- a >50% increase in bone marrow blast count percentage from the nadir and that is <math>\geq 20\%</math>.
 
 
For patients with <math>\geq 67\%</math> bone marrow blasts at nadir:
 
 
- a doubling of the nadir absolute peripheral blood blast count and the final absolute peripheral blood blast count is <math>> 10 \times 10^9/L</math>.
 

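### SAP Table 3 note 1 cancels a lone progression only when a response follows, so progression followed by stable disease stays an EFS and DOR event that the plan's own confirmation rule would not accept

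*SAP*

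**What the plan says.** **Event rules in the SAP.** Note 1 to Table 3 (SAP 10.3.1.4) gives its condition as "If response assessment after a single documented progressive disease /relapse shows response including CR, CRi, CRp, PR, mCR/MLFS" and its effect as "the relapse/progression before documented response is considered as NE". No other text tells a programmer what to do with a progression that a later assessment does not bear out. EFS (SAP 10.3.2.1) runs to "the date of documented relapse, progression, or death due to any cause, whichever occurs first". It is tied to Table 3 by two sentences: "Subjects without an EFS event will be censored according to the rules in" Table 3, and "The analysis methods for EFS are similar to those for DOR".

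**Progression criterion.** Protocol Table 8 states "Progression should be confirmed by 2 consecutive assessments separated by at least 1 month". SAP Table 7 repeats that sentence. Both date PD at the first date on which it was seen. Protocol Table 8 adds that progression is defined only for subjects who have already attained PR or SD; SAP Table 7 leaves this limit out.

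**Repeat assessment.** Protocol 10.8.3 calls for a repeat 28 days after a first PD in order to confirm it. Protocol Table 6 has one row headed "If repeat evaluation shows SD, PR, or CR" and a separate row for confirmed PD.

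**Statistical text in the protocol.** Section 12.3 says that subjects treated beyond progression count as progressed at the time of first progression in the primary efficacy analyses.

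**Declared changes.** SAP section 13 lists an added data cut-off, a change of terminology and added secondary endpoints. Confirmation of progression is not mentioned.

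**The concern.** A PD followed by SD fails the two-assessment requirement, yet note 1 leaves it standing because SD is not one of the listed responses. The EFS event is then dated at the first, unconfirmed PD. The same happens to DOR in a PR subject who goes from PD to SD. Other responders normally lose their response by relapse rather than progression, so the DOR effect is confined to PR subjects.

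Two programmers could each follow the SAP faithfully, one using note 1 and the other Table 7, and derive different EFS times for the same subject. The sensitivity analysis described in 10.3.1.4 as addressing confirmed progression does not settle this. It restores the single events that note 1 cancels, by counting a PD or relapse that is immediately followed by a response. That moves further from confirmation, and it leaves PD followed by SD untouched.

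**Working it through.** **1. The plan's own figures.** No size, power or precision figure is given for EFS or DOR. The only Phase 2 design figure is for ORR: 42/125 = 33.6%, with exact 95% CI 25.4% to 42.6%. Clopper-Pearson limits reproduce it (25.40% to 42.60%). It does not depend on this point.

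**2. One subject under both SAP rules.** The PD threshold for a nadir of 5% to 67% marrow blasts is a rise of more than 50% from nadir to a level of at least 20% (protocol Table 8, SAP Table 7). Take a subject already assessed as SD, nadir 14%, who meets no response category afterwards (illustrative values).

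| Assessment | Blasts | Change from nadir | Meets PD threshold? |
|---|---|---|---|
| Nadir (SD) | 14% | – | – |
| Next | 22% | 22/14 − 1 = +57% | Yes: above 50% and at least 20% |
| Repeat | 17% | 17/14 − 1 = +21% | No: fails both parts |

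- Note 1: SD is not a listed response, so the 22% assessment remains a documented progression and is the EFS event.
- SAP Table 7: there are not two consecutive PD assessments, so progression is not confirmed and EFS continues.

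**3. Size for EFS.** The share of subjects with PD then SD is not in the documents, so these are assumptions. Without censoring, k affected subjects among 125 can lower a later EFS rate by at most k/125.

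- 5% of 125, about 6 subjects: 6/125 = 4.8 points.
- 10% of 125, about 12 subjects: 12/125 = 9.6 points.

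These are upper limits, because some affected subjects would have a true event before the time point anyway. A simulation illustrates this. It assumes exponential EFS under the confirmed rule and an unconfirmed PD, in the stated share of subjects if still event-free, uniformly between day 56 and day 112. With a true median of 6 months:

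| Share | Median EFS (months) | 6-month EFS |
|---|---|---|
| 0% | 6.0 | 50.0% |
| 5% | 5.6 | 47.5% |
| 10% | 5.1 | 45.0% |

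With true medians of 4 and 8 months, the 6-month rate falls by 1.8 (35.3 − 33.5) and 3.0 (59.4 − 56.4) points at 5%, and by 3.5 (35.5 − 32.0) and 5.9 (59.5 − 53.6) points at 10%.

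**4. Interval.** By the SAP's conversion of 30.4 days per month, the 28-day repeat is 28/30.4 = 0.92 month. Taken literally, a repeat exactly on schedule falls short of the one-month separation in Table 7.

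**The case against.** **SAP Table 7 already requires confirmation.** If a documented progression means one that satisfies Table 7, PD then SD is no event. That reading is open, so the conflict lies inside the SAP and is not simply SAP against protocol. But if Table 7 governed, a PD followed by a response would also be no event, and note 1 would not be needed for progression. The text needs correcting on either reading.

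**Protocol 12.3 counts the first progression.** It can be read as dating a confirmed PD at its first date, which agrees with Table 8. Read instead as counting any first PD, it would also forbid the cancellation that note 1 allows. Neither reading justifies treating SD differently from a response.

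**Table 6 is guidance on assessment and treatment, and Table 3 is a DOR table.** Both are fair. Table 6 is only corroboration. Table 3 reaches EFS by cross-reference, through a sentence about subjects without an event; its use to decide what is an event should be stated.

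**Note 1 is not limited to the next assessment.** PD, then SD, then response may already be covered. The clear gap is PD then SD with no later response.

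A reader might infer more than the documents support:

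- That the SAP turns the early blast rise at C2D1 into an EFS event at about one month. Protocol Table 8 defines progression only after PR or SD, and at C2D1, the first post-baseline Phase 2 assessment, a subject has attained neither. Protocol 10.8.3 says the drug "can generate a clinical response after an initial increase in the number of immature monocytes or blast cells"; that is a rise followed by response, which note 1 rescues, and it is described as possible rather than expected.
- That no planned analysis could apply confirmation. EFS for Phase 2 and DOR are also to be analysed by IRAC assessment, and IRAC uses the modified IWG criteria (SAP 15.3, the appendix that holds Table 7). Whether its calls apply the two-assessment rule is not stated.

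**Conclusion.** The point holds as an inconsistency that changes event dates. Note 1 is the only operational rule, it omits SD, and it conflicts with the confirmation requirement in SAP Table 7 and protocol Table 8 without being declared as a change. None of the listed censoring or confirmation sensitivity analyses removes a PD followed by SD.

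Its reach is limited. EFS is among the other secondary endpoints and is estimated descriptively. DOR is a key secondary endpoint but is affected only in PR subjects. The effect on EFS is unknown; the range of up to about 5 to 10 points rests on an assumed 5% to 10% of subjects and no censoring, and the simulated effects are smaller. The direction is known: the present rule can only shorten EFS and DOR relative to a confirmed-PD rule.

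**What to change.** In SAP 10.3.1.4 (Table 3 note 1) and 10.3.2.1:

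1. State that progression for EFS and DOR follows SAP Table 7. A single PD followed at the next adequate assessment by SD or any response is not an event; a confirmed PD is dated at its first date.
2. State, as an explicit analysis convention, that a PD with no later assessment is kept as an event. This goes beyond strict confirmation, so it should be declared rather than implied.
3. State that, for the analysis, the scheduled 28-day repeat counts as meeting the one-month separation.
4. Say that the note applies to EFS, both in deciding what is an event and in censoring.
5. Reconcile the rule with protocol 12.3 and with protocol Table 8's limit to subjects with prior PR or SD, which SAP Table 7 lacks.
6. Report the present note 1 rule as a sensitivity analysis for both EFS and DOR.

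The cost is a few sentences and a small rerun. EFS and DOR will become somewhat longer, which is why the present rule should be shown beside the new one.
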